In light of these data, the aim of the current study is to test the efficacy of a fully online, Instagram-based intervention designed to reduce heavy alcohol use among young adults. Participants will be randomly assigned to either an intervention or an assessment-only control condition. Analyses will compare mean changes in past-month alcohol use, alcohol-related consequences, mindfulness, and use protective behavioral strategies in intervention versus control group participants at 10-week follow-up. Secondary analyses will assess the perceived acceptability of the intervention and its posts, as well as the degree to which the posts were seen and remembered by participants. It is hypothesized that (1) participants in the intervention group will show greater decreases in alcohol use and consequences and greater increases in mindfulness and protective behavioral strategy use than participants in the control group and (2) intervention posts will be remembered and given high acceptability ratings.

Pilot Work

The proposed project will build on a pilot study conducted by the PI between April 2021 and December 2021. During this pilot study, 50 Wayne State University students between the ages of 18-28, who reported regular binge drinking, were given an Instagram-based alcohol intervention (developed specifically for the study by the PI). After an initial orientation session, participants were asked to follow the study Instagram page and were then shown intervention posts each day for 6 weeks. A subset of participants was also exposed to a series of Instagram ‘stories’

(i.e., images that are available for viewing for twenty-four hours after posting), which were posted once every two days. Instagram content consisted of mindfulness exercises, presentation of drinking norms, information about protective behavioral strategies, and specific affirmations (described in more detail below).

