The intervention was rated as highly acceptable. Additionally, analyses revealed significant within-subjects decreases in past-month alcohol consumption, drinking days, and binge-drinking days post-intervention; however, there were no significant changes in past-month protective behavioral strategies and mindfulness practices. Although this pilot study provided critical feedback about intervention development and administration, it was intentionally small and did not include a control group, thereby limiting the interpretation of findings. The proposed study builds on this pilot work by replicating the study with a larger sample size, a community-based sample, and an assessment-only control group. Specific procedures are described below.

Chapter 2: Methods

Participants

Eighty participants will be recruited from Prolific, an online platform designed to screen and recruit potential research participants for online studies. Power analyses indicate that, with an N of 80 (two groups of 40), this study will be sufficiently powered to detect effect sizes of .20, an effect size consistent with other standalone, technology-delivered, cognitive behavioral interventions for alcohol use (Kiluk et al., 2019).

In order to be eligible for the study, participants must: (1) be a US resident, (2) be between the ages of 18 and 30; (3) report at least two binge-drinking episodes (i.e., four or more drinks in one sitting for cis women, five or more drinks in one sitting for cis men or transgender and

nonbinary individuals) per month over the past three months; (4) have an active Instagram page; and (5) report regular Instagram use (i.e., at least 2-3 times a week).

Participants will be randomized to either an intervention condition in which they will follow an Instagram page and engage with content during the six-week study period or to an assessment-only control condition in which they will be emailed assessment measures, but will not be exposed to intervention content.

Measures

Demographics will be assessed at baseline. Participants will be asked to answer questions about their sex, gender, age, race, ethnicity, sexual orientation, education level, and household income. State of residence will also be assessed.

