In order to prevent delays between baseline survey completion and the start of the Instagram intervention, subgroups of participants may be randomized to condition and exposed to the intervention in different data collection waves. Each wave will last for six weeks and will contain a total of forty-two Instagram posts and twenty-one Instagram ‘stories’ (i.e., images that are available for viewing for twenty-four hours after posting and can utilize mechanics like polls and quizzes). Intervention content will be posted once per day throughout the 6-week intervention period, alternating between posting times of approximately 8 AM EST/EDT and 8 PM EST/EDT, and intervention ‘stories’ will be posted once every two days.

10-Week Follow-Up Survey. Ten weeks after the intervention start date (and four weeks after the end of the intervention), participants will be emailed a follow-up survey, which will contain the same questionnaires as the baseline survey. Participants in the intervention condition will also be asked to rate how relevant, respectful, helpful, empathic, personalized, and interesting they felt the intervention content had been, using 5-point Likert scales. Additionally, participants in the intervention group will be shown specific examples of previously posted content and asked to rate each specific post on the dimensions listed above, as well as to indicate whether they remembered seeing those particular posts.

The follow-up survey will remain open for two weeks, and reminder messages will be sent during this time to encourage participant completion. Each participant will receive \$10 for completing the baseline session and \$15 for completing the 10-week online follow-up survey.

Analytic Strategy and Hypotheses

The data will be assessed for normality, missing data, and outliers. Data transformation, multiple imputation, and list-wise deletion will be utilized as needed. Mixed repeated-measure ANOVAs will be used to analyze within- and between-group differences in participants' alcohol consumption, alcohol-related consequences, mindfulness practices, and use of protective behavioral strategies at baseline and 10-week follow-up. Average acceptability ratings will be calculated using group means.

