We predict that (1) intervention participants will show greater decreases than control group participants in past-month quantity and frequency of alcohol use, binge-drinking episodes, and alcohol-related consequences, and (2) intervention participants will show greater increases than control group participants in the use of protective behavioral strategies and mindfulness practices. We also predict that the intervention as a whole, and specific intervention posts will be remembered and rated as highly acceptable across several dimensions (i.e., relevant, respectful, helpful, empathic, personalized, and interesting).

Figures

Figure 1. Standardized Drink Infographic

Figure 2. Example of TLFB Calendar

**12 fl oz of
regular beer**

=

**8–9 fl oz of
malt liquor
(shown in a
12 oz glass)**

about 5%
alcohol

about 7%
alcohol

**5 fl oz of
table wine**

=

about 12%
alcohol

**1.5 fl oz shot of
80-proof spirits
(whiskey, gin, rum,
vodka, tequila, etc.)**

about 40%
alcohol

The percent of “pure” alcohol, expressed here as alcohol by volume (alc/vol), varies by beverage.

December 2022

Sunday	Monday	Tuesday	Wednesday	Thursday	Friday	Saturday
				1	2	3
4	5	6	7	8	9	10
11	12	13	14	15	16	17
18 Hanukkah Begins	19	20	21 Winter Solstice	22	23	24 Christmas Eve
25 Christmas Day	26 Hanukkah Ends / Boxing Day	27	28	29	30	31

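### Adjusting the 10-week value for baseline would usually give a tighter treatment estimate than the planned two-time-point ANOVA, at almost no cost

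*Combined protocol and SAP*

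**What the plan says.** The analysis section (Analytic Strategy and Hypotheses) specifies that "Mixed repeated-measure ANOVAs will be used to analyze within- and between-group differences" in drinking, consequences, mindfulness and protective strategies, measured "at baseline and 10-week follow-up". The aim paragraph at the end of Instagram Interventions sets the contrast: "Analyses will compare mean changes in past-month alcohol use, alcohol-related consequences, mindfulness" and protective strategies between arms. The hypotheses point the same way: "intervention participants will show greater decreases than control group participants in past-month quantity and frequency of alcohol use", with further outcomes listed after it. Read together, these make the group-by-time interaction the efficacy test.

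The follow-up survey is one "which will contain the same questionnaires as the baseline survey" (Procedure, 10-Week Follow-Up Survey), so every efficacy outcome has its own baseline measurement. Nowhere is that measurement used as a covariate.

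Participants (Chapter 2) gives 80 people in two groups of 40 and states that "this study will be sufficiently powered to detect effect sizes of .20". It does not give the metric of that effect size, the alpha, a numeric power, an SD, a correlation or a dropout rate.

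**The concern.** A change score subtracts the whole baseline value, which fixes the regression slope on baseline at 1. The data will usually support a smaller slope, and the excess subtraction adds noise. A model that estimates the slope removes that noise.

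This matters because the trial is small. With 40 per arm, the difference in baseline means that arises by chance has a standard error of sqrt(2/40) = 0.22 SD. Given such an imbalance, the change score is displaced by (rho × k − 1) times its size, where rho is the baseline-to-follow-up correlation and k is the follow-up SD divided by the baseline SD. Under a linear relationship the adjusted model removes that displacement. At stake are wider confidence intervals than the collected data require.

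**Working it through.** **The plan's own figure.** The claim for .20 with N = 80 cannot be reproduced as it stands, because metric, alpha, power and rho are missing. With two-sided alpha 0.05 (assumed):

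- As a standardised mean difference, a comparison of follow-up values alone has 14% power, and 80% power needs 393 per arm. The change-score test has 12%, 14% and 21% power at rho 0.3, 0.5 and 0.7.
- As Cohen's f for the interaction, noncentrality is f² × N × 2/(1 − rho), and power is 85%, 94% and 99.5% at the same rho values. Equating this with the change-score noncentrality, d² × 20/[2(1 − rho)], gives d = 4f. So f = .20 means a difference in change of 0.80 baseline SD.

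The comparison below does not depend on which reading was meant.

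**Inputs.** From the documents: two time points, 1:1 allocation, N = 80. Assumed: rho from 0.3 to 0.9; k of 0.8, 1 or 1.25, the same in both arms; 80 or 60 completers. Values of k above 1 cannot be excluded, because entry requires that people "report at least two binge-drinking episodes" per month and no such floor applies at follow-up.

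**Formulas**, in units of baseline variance:

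- Change score: variance proportional to 1 + k² − 2 × rho × k.
- Baseline-adjusted: variance proportional to k²(1 − rho²) × (N − 3)/(N − 4). The last factor is the price of estimating the slope: 77/76 = 1.0132 for N = 80 and 57/56 = 1.0179 for N = 60.
- Before that factor, change minus adjusted equals (1 − rho × k)². This is never negative, and it is zero only at rho × k = 1.

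Example with k = 1, rho = 0.5: adjusted 0.75 × 1.0132 = 0.760, change 1.00, so the variance is 24% lower.

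**Variance ratio, adjusted to change score, 80 completers:**

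| k | rho 0.3 | 0.5 | 0.7 | 0.8 | 0.9 |
|---|---|---|---|---|---|
| 0.8 | 0.509 | 0.579 | 0.636 | 0.648 | 0.616 |
| 1 | 0.659 | 0.760 | 0.861 | 0.912 | 0.962 |
| 1.25 | 0.795 | 0.905 | 0.994 | 1.013 | 0.962 |

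The variance falls in 14 of the 15 cells, by 0.6% to 49%. In the remaining cell, where rho × k = 1, it rises by 1.3%. With 60 completers the ratios move by at most about half a percentage point, and that cell becomes 1.018.

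Simulation with 40,000 normal trials per cell agreed: 0.658, 0.760 and 0.862 for k = 1 at rho 0.3, 0.5 and 0.7, and 1.011 in the worst cell. Both estimators were unbiased when baseline was unaffected by arm. In a separate simulation without a treatment effect, the change-score test had a type I error of 4.8% to 5.0%.

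**Difference detectable with 80% power, in baseline SD** (noncentral t, 78 and 77 degrees of freedom):

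| k, analysis | rho 0.3 | 0.5 | 0.7 | 0.8 | 0.9 |
|---|---|---|---|---|---|
| 1, change | 0.751 | 0.634 | 0.491 | 0.401 | 0.284 |
| 1, adjusted | 0.609 | 0.553 | 0.456 | 0.383 | 0.278 |
| 1.25, change | 0.854 | 0.727 | 0.572 | 0.476 | 0.355 |
| 1.25, adjusted | 0.761 | 0.691 | 0.570 | 0.479 | 0.348 |

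In sample-size terms, for k = 1 and rho 0.3, 0.5 and 0.7, the adjusted analysis of 80 people matches a change-score analysis of about 80/0.659 = 121, 80/0.760 = 105 and 80/0.861 = 93.

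**Power at 0.20 baseline SD, k = 1:** from 12% to 15%, 14% to 17%, 21% to 23%, 29% to 31% and 51% to 52% across the five rho values. The highest adjusted power in the grid is 71% (k = 0.8, rho = 0.9).

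**The case against.** The strongest objection concerns validity. Under Recruitment and Baseline, people allocated to the intervention first agree to the page rules. They then receive the baseline questionnaires together with the page link and are told to follow the page at once. Their baseline answers may therefore be given with allocation known. If allocation shifts reported baseline by b SD, the change score is biased by b and the adjusted estimate by the slope times b, which is rho × b with equal SDs. This stands as a condition on both analyses. Adjustment shrinks the bias whenever rho × k is below 1, but does not remove it. Where rho × k exceeds 1 (1.125 at k = 1.25, rho = 0.9) the bias is slightly larger.

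Second, no figure for the gain comes from the documents, and the equal-SD case is the more favourable one. That is so: in the k = 1.25 row, the gain at rho 0.5, 0.7 and 0.8 is 9.5%, 0.6% and a 1.3% loss. The direction of the argument does not depend on the assumed values, because the possible loss is bounded and small.

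Third, the aim speaks of mean changes and the plan intends within-group analysis. Neither is an obstacle. Regressing the change on arm and baseline gives exactly the same arm coefficient as regressing the follow-up value, and within-group results can still be reported.

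Skewed counts and missing follow-up, for which the plan says "Data transformation, multiple imputation, and list-wise deletion will be utilized as needed", are separate matters that baseline adjustment does not settle.

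**Conclusion.** The point holds as a nearly free improvement; the planned test is not an error. Baseline adjustment usually gains precision. The size is unknown until rho and the SD ratio are known. The headline reductions of 34%, 24% and 14% rest on equal SDs, 80 completers and rho of 0.3, 0.5 and 0.7. The gain is near zero when rho × k is close to 1, and the worst-case loss is 1.3% more variance with 80 completers or 1.8% with 60.

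It does not rescue the sample-size statement if .20 there is a standardised mean difference. If .20 is Cohen's f, the planned test is already adequately powered at the rho values computed, and adjustment would mainly narrow the intervals.

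**What to change.** Under Analytic Strategy and Hypotheses, replace the ANOVA sentence with wording such as: 'For each outcome (alcohol consumption, alcohol-related consequences, mindfulness and protective strategies), the treatment effect is the between-arm difference at 10 weeks from a linear model of the follow-up value on arm and the baseline value of that outcome, both on the same scale if transformed, with a 95% confidence interval. Within-group changes will also be reported; they are not the efficacy test.'

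In the aim paragraph, add that the comparison of changes is made with adjustment for baseline, so that the two places agree. State in the Procedure section whether the baseline questionnaires are completed before allocation is disclosed, since both analyses depend on it.

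The cost is one or two sentences of analysis wording, the two small clarifications and one degree of freedom, with no new data. Within-group results are kept but become descriptive. The change should be made and dated before outcome data are examined.

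### One efficacy aim is tested on six predicted measures with no primary outcome, significance level or success rule, so what would count as efficacy is left open

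*Combined protocol and SAP*

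**What the plan says.** The closing paragraphs of the Instagram Interventions section give a single aim, "to test the efficacy of a fully online, Instagram-based intervention designed to reduce heavy alcohol use among young adults". They then list four outcome domains without ranking them: alcohol use, consequences, mindfulness and protective strategies. A ranking label appears once, in the same place: "Secondary analyses will assess the perceived acceptability of the intervention and its posts", together with how far posts were seen and remembered.

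The Analytic Strategy and Hypotheses section applies mixed repeated-measures ANOVAs to "alcohol consumption, alcohol-related consequences, mindfulness practices, and use of protective behavioral strategies at baseline and 10-week follow-up". It then predicts, as hypothesis (1), "greater decreases than control group participants in past-month quantity and frequency of alcohol use, binge-drinking episodes, and alcohol-related consequences", and as hypothesis (2) that "intervention participants will show greater increases than control group participants in the use of protective behavioral strategies and mindfulness practices".

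The two sections do not divide the outcomes in the same way. The study aim puts drinking, consequences, mindfulness and strategies into one hypothesis and makes acceptability and recall the second. The Analytic Strategy splits drinking and consequences from strategies and mindfulness.

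The Participants section says of 80 people in two groups of 40 that "this study will be sufficiently powered to detect effect sizes of .20". It does not name the outcome, the effect-size metric, the significance level or the power. Nothing in the text available names a primary outcome, a significance level, a multiplicity method or a success rule.

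**The concern.** The trial is meant to support one conclusion, that the intervention works or that it does not, but nothing in the plan maps six test results onto that conclusion. If a favourable result on any one measure can be read as efficacy, the false-positive rate of the conclusion exceeds that of a single test. If every measure must succeed, the rate is much lower when nothing works, but one unresponsive measure defeats the claim. The plan does not choose between these rules, so the text leaves room to choose after the results are known.

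A mixed result is a realistic prospect. The uncontrolled pilot reported significant falls in consumption, drinking days and binge-drinking days, whereas "there were no significant changes in past-month protective behavioral strategies and mindfulness practices". The pilot cannot show what a randomized comparison will find; it shows only that drinking and process measures may diverge. The plan gives such a split no consequence for the efficacy conclusion.

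**Working it through.** **Count of measures.** The Analytic Strategy predicts quantity, frequency, binge episodes and consequences (4), plus strategies and mindfulness (2): 4 + 2 = 6. Its ANOVA sentence lists four domains, so the number of efficacy tests could be four or six, or more if quantity is scored in several ways.

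**Assumptions, because the plan gives no values.** Each test is two-sided at .05, so one test favours the intervention by chance with probability .025. No measure has a true effect. Correlations between test statistics are taken over a range.

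**Any one measure suffices: independent tests as an upper reference.**
- Six measures: 1 − .975^6 = .141
- Four measures: 1 − .975^4 = .096

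Independence is not realistic here. Quantity, frequency and binge episodes are all scored from the same 30-day Timeline Follow-Back calendar.

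**Any one measure suffices: plausible correlations.** Simulated multivariate normal test statistics, 2,000,000 draws. Here rd is the correlation among the three calendar measures, rc their correlation with consequences, and ro the correlation of every pair involving strategies or mindfulness.

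| rd | rc | ro | any of six | any of four |
|---|---|---|---|---|
| .5 | .3 | .1 | .125 | .082 |
| .7 | .3 | .1 | .118 | .075 |
| .9 | .3 | .1 | .108 | .063 |
| .5 | .5 | .3 | .114 | .078 |
| .7 | .5 | .3 | .108 | .071 |
| .9 | .5 | .3 | .099 | .060 |

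That is about 10% to 13% for six and 6% to 8% for four, against 2.5%. As multiples, .099/.025 = 4.0 to .125/.025 = 5.0 for six, and .060/.025 = 2.4 to .082/.025 = 3.3 for four.

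**All measures must succeed.** With one common correlation r and no true effect anywhere, the chance that all four favour the intervention is .0030 at r = .7 and .0094 at r = .9. For all six it is .0016 and .0074. All are below 1%. This holds only if nothing works: with three large true effects, one null measure and r = .5, the chance of wrongly passing all four is .025, the single-test level.

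**The stated effect size of .20.** The plan's power claim cannot be reproduced, because metric, outcome, significance level and power are all missing. Two readings follow, with 40 per arm, two-sided .05, no attrition and baseline-to-follow-up correlation ρ = .5 (assumed).
- *Standardized mean difference, d = .20 in raw SD units.* SD of change = √(2(1 − .5)) = 1. Noncentrality = .20/√(2/40) = .894. Power is about 14%.
- *Cohen's f = .20 for the interaction.* λ = f² × N × 2/(1 − ρ) = .04 × 80 × 2/.5 = 12.8, with 1 and 78 degrees of freedom. Power is about 94%.

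These are not the same effect. For a difference in change of d raw SD, λ = d²/(2/40) = 20d² at ρ = .5. Setting 20d² = 12.8 gives d = .80, four times .20.

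**The case against.** The strongest reply is that the hierarchy is implicit. The aim is to reduce heavy drinking, so the Analytic Strategy's hypothesis (1) carries efficacy, and strategies and mindfulness are process measures. That is a natural reading, but it does not settle the matter. Hypothesis (1) still bundles four measures without saying whether one, some or all must succeed, and the study-aim paragraph places mindfulness and strategies in the same hypothesis as drinking.

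A second reply concerns size. A reader might infer from the independent-test figure that the error rate is nearly six times nominal (.141/.025 = 5.6). The documents do not support that as the expected size, since three of the six measures come from one calendar. The mixed-correlation figures are the better guide, and they too rest on assumed inputs.

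Third, a reader might infer that an all-must-succeed rule would be safe, or that the trial is either badly underpowered or amply powered at .20. Neither follows. The first holds only if no measure has a true effect, and the second compares effects that differ fourfold.

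Finally, a primary outcome may be named in a registry record or in opening material that is not in the text available. The point is therefore limited to that text, and it is no evidence that anyone intends to choose a rule after the fact.

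**Conclusion.** The concern stands in this form: in the text available, one efficacy aim is served by six predicted measures with no primary outcome, significance level, multiplicity control or success rule, and the two statements of the hypotheses differ on which measures belong together. The absence is certain as far as that text goes. Its size is conditional on the assumed two-sided .05 per test, no true effect and the stated correlation ranges. On those terms the any-one-measure reading raises the chance of a false efficacy claim to roughly four to five times the single-test level for six measures, or two to three times for four. This should be settled before follow-up data are examined. The power figures do not show that 80 participants are too few or enough; they show that the statement about .20 cannot be assessed until its outcome and metric are given.

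**What to change.** Before any follow-up outcome data are examined:

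1. Name one drinking measure from the Timeline Follow-Back as primary. Binge-drinking days is one candidate: it fits the introduction's description of a binge-drinking intervention and can be scored from daily counts with the eligibility threshold, "four or more drinks in one sitting for cis women, five or more drinks in one sitting for cis men" (the five-drink limit also covers transgender and nonbinary participants). It needs a statement that a calendar day stands in for a sitting. Another single drinking measure would close the gap equally well.
2. Test its group-by-time interaction at two-sided .05 and state that the efficacy conclusion rests on that test.
3. Report the remaining measures as secondary, either Holm-adjusted or labelled supportive, and align the hypotheses in the study aim with those in the Analytic Strategy.
4. Restate the power claim for the primary outcome, giving the metric behind .20, the significance level, the power, the assumed baseline-to-follow-up correlation and the attrition allowance.

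The cost is protocol wording and one restated power calculation; no new data are needed. There are two downsides. A lone significant secondary result can no longer be presented as efficacy, and the restated calculation may show low power if .20 was meant as a standardized mean difference.
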